Rationale: Intra-abdominal pressure (IAP) needed to create sufficient workspace during laparoscopic surgery affects the surrounding organs with ischemia-reperfusion injury and a systemic immune response. This effect is related to postoperative recovery, pain scores, opioid consumption, bowel function recovery, morbidity and possibly mortality. In clinical practice standard pressures of 12-16mmHg are applied instead of the lowest possible IAP, but accumulating evidence shows lower pressure pneumoperitoneum (PNP) (6-8mmHg) to be non-compromising for sufficient workspace, when combined with deep neuromuscular blockade (NMB) in a vast majority of patients. Therefore, low impact laparoscopy, meaning low pressure PNP facilitated by deep NMB, could be a valuable addition to Enhanced Recovery After Surgery (ERAS) Protocols.

Increased IAP can cause peritoneal mesothelial injury either directly or by compression of small vessels including capillaries, leading to a variable degree of ischemia reperfusion injury. The compromised perfusion of the parietal peritoneum can be visualized and quantified by a fluorescent marker such as Indocyanine green (ICG), as shown in a previous pilot study. Hypoxic injury of intra-abdominal organs and/or tissues may cause the release of Danger Associated Molecular Patterns (DAMPs). It is known that after trauma and sepsis, the release of DAMPs is associated with immunoparalysis and a higher susceptibility to infectious complications. The use of low pressure PNP may reduce hypoxic injury and the release of DAMPs and thereby contributing to a better preservation of innate immune function which may help to reduce the risk of infectious complications.

Objective:

Primary objectives:

- To establish the relationship between the use of deep neuromuscular blockade (NMB) with low pressure pneumoperitoneum (PNP) and the quality of recovery after RARP.
- To establish the relationship between the use of deep neuromuscular blockade (NMB) with low pressure pneumoperitoneum (PNP) and innate immune function after RARP.

Secondary objectives:

- To study whether low pressure PNP and/or deep NMB affects the perfusion of the parietal peritoneal layer during RARP.

Study design: A mono-center, randomized controlled clinical trial.

Study population: Adult patients undergoing elective RARP without extended lymph node dissection.

Intervention: The participants will be randomly assigned in a 1:1 fashion to:

- A. Experimental group: low impact laparoscopy (low pressure (8 mmHg) and deep NMB (PTC 1-2))

B. Control group: standard laparoscopy (standard pressure (14 mmHg) and moderate NMB (TOF 1-2))

At the start of surgery, after intra-abdominal insufflation, ICG injection will take place to quantify *parietal peritoneum* perfusion, and a parietal peritoneal biopsy will be taken. At the end of surgery, a second parietal peritoneum biopsy will be taken.

Main study parameters/endpoints:

Primary endpoints

- Quality of recovery score (QoR-40) at postoperative day 1.
- IL-6 and IL-10 response upon whole blood LPS stimulation at postoperative day 7.
- Perfusion index of the parietal peritoneum as calculated from the slope of ICG fluorescence intensity, and time to maximal intensity in seconds. (extracted from video registration).

Secondary endpoints

- QoR-40 score (day 1 and day 10-12), SF-36 score (1 day before, 10-12 days and 3 months after surgery), McGill pain questionnaire (3 months after surgery).
- Pain scores, analgesia use, PONV, time to reach discharge criteria, length of hospital stay, surgical conditions and postoperative complications scored by Clavien Dindo classification (table 2 (1)).

Nature and extent of the burden and risks associated with participation:

The use of a deep NMB enables the safe use of low-pressure PNP. If despite a deep NMB visibility is compromised, pressure will be increased to minimize surgery related risks. A deep NMB is achieved by higher doses of rocuronium which are within normal therapeutic range used in clinical practice, and is safe to use. Depth of NMB will be monitored throughout the whole surgery. At the end of surgery, the effects of rocuronium will be antagonized by sugammadex to avoid residual paralysis. Indocyanine green is a registered product routinely used to quantify tissue perfusion during this surgery. The total dose during surgery is below the advised maximum dose of 5 mg/kg. Any possible risk factors or interactions as mentioned in the Summary of Product Characteristics are covered by exclusion criteria in order to fully eliminate risk of participation. Regarding the peritoneal biopsies; peritoneal tissue is directly visible and easily accessible during laparoscopic surgery and biopsies are obtained in a standardized manner with hemostasis when needed under direct vision. Therefore, no additional complications are expected. Blood samples will be combined with routine laboratory assessment where possible. Previous studies have shown low-pressure PNP is associated with reduced postoperative pain scores, reduced opioid consumption and improved bowel function. This may lead to enhanced recovery. The burden for participants is mainly related to the evaluation of the endpoints during the early postoperative phase. Assessment of pain scores, nausea, complications and discharge criteria are part of the normal treatment. Questionnaires will take approximately 10-15 minutes per time-point.

1 INTRODUCTION AND RATIONALE

Release of DAMPs in surgical patients

By induction of a pneumoperitoneum with carbon dioxide (CO₂) a surgical field is created for laparoscopic surgery. A sufficient surgical field is important because of the intra-operative complications related to a limited workspace, although the side-effects of an increased IAP are just as important, but not directly present. The pressure to maintain a sufficient workspace affects the surrounding organs and vasculature. Standard PNP (usually 12-14 mmHg) causes a temporarily decreased perfusion leading to ischemia-reperfusion injury with oxidative stress and release of Danger Associated Molecular Patterns (DAMPs) (2-7). DAMPs elicit an immune response of innate immune cells, which results in a systemic inflammatory response syndrome (SIRS) followed by a compensatory anti-inflammatory reaction (8). This response causes sensitization of nociceptors enhancing postoperative pain, the anti-inflammatory reaction is related to fatigue and leaves more susceptibility for infections (9-11). Maca et al. shows the relation between DAMPs and the degree of surgical trauma, and predicted morbidity and mortality after elective major abdominal surgery (12). Fragidiakis et al described a strong correlation between immune status and recovery from surgery. Signaling responses downstream in monocytes were particularly strong correlates of recovery outcomes including pain and fatigue (13).

Upon (surgical) trauma DAMPs e.g. nuclear DNA, Heat Shock Protein-70, mitochondrial DNA, are released and bind to receptors on immune cells such as macrophages, which induces an anti-inflammatory response predominantly characterized by IL-10 release. In turn this leads to immune suppression, reflected by decreased monocytic HLA-DR expression as well as reduces production of TNF-alpha and IL-6 and increased production of IL-10 upon ex vivo stimulation with LPS (figure 1 (14)).

Alternatively, DAMPs can exert direct immunosuppressive effects, such as HSP10-induced LPS-tolerance in monocytes. All these events take place in a very early phase after surgery.

[figure not shown]

Figure 1. Adapted from Timmermans *et al.* (14)

Low pressure PNP and immune homeostasis after surgery

Accumulating evidence shows the safety and advantages of low-pressure PNP (6-8mmHg); clinically relevant reduction in postoperative pain (15,16), reduced cumulative opioid consumption (17) and improved bowel function (16,18). Furthermore, it preserves innate immune homeostasis, reflected by reduced increase in pro-inflammatory mediators IL-6, IL-10 and TNF-alfa (19–22). And a reduced decrease in monocytic HLA-DR expression (19). Therefore, it is of clinical importance to elucidate the relation between the degree of PNP with its peritoneal and organ perfusion and preservation of innate immune function, to enhance postoperative recovery.

A limited number of studies investigated the immune response after low pressure laparoscopy. It was found that low pressure pneumoperitoneum was associated with a reduced increase in serum levels of pro-inflammatory cytokines like IL-6 and TNF-alpha (19–21) and also with lower levels of anti-inflammatory IL-10 (22). Moreover, Schietroma *et al.* also described a better preservation of monocyte function as reflected by higher levels of HLA-DR expression on monocytes (19). Altogether this provides indirect evidence that lower intra-abdominal pressures may contribute to recovery by a reduced stress response and subsequently a better preservation of innate immune function as compared to laparoscopy with higher intra-abdominal pressures. The interim-analysis of the RECOVER PLUS study showed that patients undergoing laparoscopic colorectal surgery showed a reduced *ex vivo* TNF- α and IL-6 response upon whole blood stimulation at postoperative day 1 which reflects immune suppression due to surgical trauma (Figure 2) (23).

[figure not shown]

Figure 2. Preliminary/interim results from the RECOVER PLUS study. After *ex vivo* stimulation of whole blood, the release of TNF- α and IL-6 is significantly reduced at POD 1. In patients allocated to low pressure PNP with deep NMB, TNF- α release is almost restored as compared to baseline. This indicates that low pressure with deep NMB is associated with better preservation of immune function after laparoscopic colorectal surgery. (23)

Patients allocated to low pressure PNP with deep NMB the TNF- α response was almost restored to baseline at postoperative day 3, whereas patients allocated to standard pressure with moderate NMB showed ongoing immune suppression.

To ensure the safety of low-pressure PNP, deep NMB facilitates a sufficient surgical field. Several studies show a significant reduction in IAP with deep NMB compared to moderate NMB, without compromising surgical conditions in patients undergoing laparoscopic surgery (18,24). Current evidence indicates a reduction of 3-4mmHg of IAP when deep NMB is used, with a sufficient and safe surgical field measured and quantified by Leiden-surgical-rating-scale (L-SRS) (25).

Low pressure PNP improves intra-abdominal perfusion

Our group performed the PERFUSION study in which patients undergoing robot assisted laparoscopic colorectal surgery were allocated to an intra-abdominal pressure of 8, 12, or 16 mmHg. Subsequently fluorescence of the parietal peritoneum was recorded after injection of a standardized dose of indocyanine green (26). The time to maximum fluorescent intensity was significantly lower in patients allocated to 8 mmHg. Also, the maximal fluorescent intensity was significantly lower at 8 mmHg as compared to 12 and 16 mmHg (Figure 3). These data indicate that perfusion of intra-abdominal organs and/or tissues is better below 12 mmHg.

Figure 3. Recordings of the parietal peritoneum after injection of a bolus of indocyanine green. The images are typical examples of three patients representing the mean time to maximum fluorescent intensity at 8, 12 and 16 mmHg. (26)

[figure not shown]
[figure not shown]

Figure 4. Preliminary/interim results from the RECOVER PLUS study. The increase in expression of HIF-1α in peritoneal biopsy after laparoscopic colorectal surgery compared to the intra-abdominal pressure used. Values are presented as means with standard error of the mean. 8 mmHg (n=4), 10 mmHg (n=3), 12 mmHg (n=12). (26)

Biopsies of the parietal peritoneum were taken after trocar introduction and at the end of surgery. Patients who underwent surgery with a pneumoperitoneum pressure of 8 or 10 mmHg showed lower expression of Hypoxia Induced Factor-1a as compared to those with an intra-abdominal pressure of 12 mmHg. These data support the hypothesis that the use of intra-abdominal pressures below 12 mmHg leads to an improved perfusion of intra-abdominal organs and tissues and thereby reducing hypoxia and ischemic injury.

The aim of this study is to assess the mechanisms and impact of low pressure on:

- perfusion of the parietal peritoneum,
- tissue markers of ischemia and inflammation in the parietal peritoneum,
- serum cytokines and DAMP's,
- ex vivo innate immune function,
- clinical outcomes i.e. pain scores, quality of recovery and (infectious) complications.

The study is designed to reveal the precise mechanism underlying the clinical benefits of the use of low-pressure PNP facilitated by deep NMB.

2 OBJECTIVES

Primary objectives:

- To establish the relationship between the use of deep neuromuscular blockade (NMB) with low pressure pneumoperitoneum (PNP) and the quality of recovery after RARP.
- To establish the relationship between the use of deep neuromuscular blockade (NMB) with low pressure pneumoperitoneum (PNP) and immune function after RARP.

Secondary objectives:

[figure not shown]
- To study whether low pressure PNP and/or deep NMB affects the perfusion of the parietal peritoneal layer during RARP.

3 STUDY DESIGN

A mono-center blinded randomized controlled clinical trial at the Canisius Wilhelmina Hospital in Nijmegen, where approximately 300 robot assisted radical prostatectomy (RARP) procedures are performed annually. We expect that the screening and inclusion period (recruitment period) will be 15 months.

Treatments to be compared

- Experimental group: *Low impact laparoscopy*; low pressure PNP (8 mmHg) and deep NMB and reversal of NMB with sugammadex 4mg/kg.

- Control group: *Standard laparoscopy*; standard pressure PNP (14 mmHg) and moderate NMB and spontaneous recovery of neuromuscular function (only if one or more additional boluses of rocuronium are required, it is allowed to reverse with sugammadex 2mg/kg)

All study endpoints will be arbitrated by a blinded researcher. Also the perfusion index is extracted from video registration with MATLAB (R2017a version 9.2.0) by a researcher blinded to the level of pressure and NMB depth.

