- After introduction of the camera trocar, insufflation of carbon dioxide is titrated to an IAP of 8mmHg in the experimental group, and 14 mmHg in the control group. After placement of the last trocar the injection of ICG and video registration of peritoneum will take place, and a peritoneal biopsy will be taken. There after surgery will take place, for dissection of the venous plexus, IAP is titrated to 14 mmHg in the experimental group and 20mmHg in the controle group. A second parietal peritoneum biopsy will be taken at the end of surgery. If surgical conditions remain compromised despite adequate pressure and neuromuscular block, the surgeon can decide to convert to an open- or hand-assisted procedure.
- Neuromuscular monitoring is initiated after set-up and calibration procedures.
 - The control group with standard laparoscopy will be monitored with TOF count every 5 minutes in standardized fashion. After intubation, a bolus or continuous infusion of rocuronium is administered as normally done in clinical practice, titrating towards TOF count 1-2. When TOF count is 0, infusion of rocuronium will be stopped until neuromuscular function is recovered to maximal TOF 2.
 - The experimental group with low impact laparoscopy will be monitored with PTC every 5 minutes. After intubation, continuous infusion of rocuronium (0,3-0,4mg/kg) is started and titrated towards PTC 1-2. When PTC is 0, continuous infusion of rocuronium will be decreased, not stopped, until a PTC of 1-2 is reached.
- During surgery patients are ventilated by pressure-regulated volume-controlled ventilation through an endotracheal tube with a mixture of oxygen in air, PEEP of 5cmH₂O and tidal volumes between 6-8ml/kg. Minute ventilation is adjusted to main end-tidal carbon dioxide between 31-43mmHg by changing respiratory rate. Oxygenation is adjusted to main saturation between 97-100% by changing the mixture of oxygen in air.
- According to local protocol a nasogastric tube will be placed for gastric decompression.
- Minimal infusion of fluids and losses will be replaced.
- Core temperature is measured continuously, aiming at 36-37 C.
- The use of drains is avoided

- After skin closure, the NMB is reversed using sugammadex 4mg/kg in the experimental group, and 2mg/kg in the control group unless the TOF ratio is >0,9. If neuromuscular function has recovered spontaneously in the control group, no sugammadex will be administered.

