- Extubation will be performed when TOF ratio is stable at >0,9 for more than 2 minutes and the patient is fully awake.

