7.6 Dosages, dosage modifications and method of administration

- a. Rocuronium: in both groups, a bolus of 0.6 mg/kg rocuronium is administered intravenously before tracheal intubation. After tracheal intubation, in group A (low pressure with deep NMB), a bolus of 0.6 mg/kg rocuronium is administered and continuous infusion of rocuronium (0.4 mg/kg) is started and titrated towards PTC 1-2. In group B (normal pressure with moderate NMB), a bolus or continuous infusion of rocuronium is administered, titrating towards a TOF count of 1-2. Dosage in both groups is within normal therapeutical range used in clinical practice (28).
- b. Sugammadex: if TOF-ratio is <0.9 the NMB is reversed with an intravenous bolus injection of 2 (moderate NMB) or 4 (deep NMB) mg/kg. If TOF-ratio > 0.9 the patient can be extubated safely (29).

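### Three treatment rules are inconsistent or unworkable as written: control-arm reversal, rescue pressure in group B, and group A rocuronium dosing

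*Combined protocol and SAP*

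**What the plan says.** **Control reversal.** Section 3, under the treatments to be compared, defines the control arm as standard pressure with "moderate NMB and spontaneous recovery of neuromuscular function" and adds the exception "only if one or more additional boluses of rocuronium are required, it is allowed to reverse with sugammadex 2mg/kg". Section 5.1 sets the dose after skin closure at "2mg/kg in the control group unless the TOF ratio is >0,9", and continues: "If neuromuscular function has recovered spontaneously in the control group, no sugammadex will be administered". Section 7.6 says "if TOF-ratio is <0.9 the NMB is reversed with an intravenous bolus injection of 2 (moderate NMB) or 4 (deep NMB) mg/kg". On maintenance of the control block, 5.1 says "After intubation, a bolus or continuous infusion of rocuronium is administered as normally done in clinical practice, titrating towards TOF count 1-2"; 7.6 likewise allows bolus or infusion. For both arms, 5.1 adds: "Extubation will be performed when TOF ratio is stable at >0,9 for more than 2 minutes".

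**Rescue pressure.** Section 8.3 raises pressure by 2 mmHg when the surgical rating is 3 or lower. The ceiling is 14 mmHg for groups A and B and 16 mmHg for groups C and D. Section 5.1 starts group A at 8 mmHg and group B at 14 mmHg. It separately plans a rise to 14 and 20 mmHg respectively for the venous plexus dissection.

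**Group A rocuronium.** Both arms receive 0.6 mg/kg for intubation. For group A after intubation, 7.6 then says "a bolus of 0.6 mg/kg rocuronium is administered and continuous infusion of rocuronium (0.4 mg/kg) is started and titrated towards PTC 1-2". Section 5.1 has only an infusion of 0.3 to 0.4 mg/kg, titrated to the same target. Neither section gives the infusion per hour, although 7.3 and 7.5 do.

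**The concern.** Section 3 decides reversal in controls by whether extra boluses were given; 5.1 and 7.6 decide it by the measured TOF ratio. Because section 3 lists reversal as part of the control treatment, one element of the comparator has two definitions. Two controls with the same unrecovered ratio at skin closure are treated differently under section 3, depending on how the block was maintained, and alike under 5.1 and 7.6.

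This also affects data handling. Section 10 requires protocol violations to be identified before unblinding. An unrecovered, infusion-only control who is given 2 mg/kg complies with 5.1 and 7.6 but departs from section 3. If he is left to recover unaided, the position is reversed. Violations cannot be classified consistently until one rule governs.

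The rescue rule refers to arms that do not exist and, for group B, triggers an action that cannot be taken. For group A, the two dosing texts give different instructions on whether a second bolus is due.

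**Working it through.** **1. Control reversal, by patient state at skin closure**

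| Control patient | Section 3 | Sections 5.1 and 7.6 | Result |
|---|---|---|---|
| TOF ratio above 0.9 | spontaneous recovery is the default | no reversal needed | agree |
| Not recovered, at least one additional bolus | 2 mg/kg allowed | 2 mg/kg given | compatible |
| Not recovered, infusion only | 2 mg/kg not allowed, read literally | 2 mg/kg given | conflict |
| Not recovered, intubation dose only | 2 mg/kg not allowed | 2 mg/kg given | conflict |

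The third row is foreseeable: 5.1 names infusion as an alternative to bolus and says how to stop and restart it in controls. The fourth row is implied by section 3 itself, since its condition supposes that some controls will need no additional bolus. Sections 5.1 and 7.6 agree in substance and differ only at a ratio of exactly 0.9.

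Number of controls in the two conflicting rows: not derivable. The only bounds are 0 and 48 of 48, and no share is assumed.

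**2. Rescue steps available (cap minus start, divided by 2 mmHg)**

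- Group A: (14 − 8)/2 = 3 steps.
- Group B: (14 − 14)/2 = 0 steps.

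The trigger in group B therefore produces no pressure change. What remains is titration of the block (8.3) and, if conditions stay poor despite adequate pressure and block, conversion (5.1).

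**3. Group A bolus total**

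- Section 5.1: 0.6 mg/kg.
- Section 7.6: 0.6 + 0.6 = 1.2 mg/kg.
- Difference: 0.6 mg/kg.

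**4. Sample size, as background**

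With n per group = 2 × (z for alpha/2 + z for power)² × (SD/difference)², rounded up, and two-sided tests assumed because section 4.4 does not state sidedness:

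- QoR-40: 2 × (1.960 + 1.282)² × (15/10)² gives 48, as stated.
- IL-6: 2 × (2.241 + 1.282)² × (4000/3000)² gives 45, as stated.
- IL-10: 2 × (2.241 + 1.282)² × (65/50)² gives 42, as stated.

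No reversal, rescue or bolus rule enters these formulas, so aligning the text changes none of them.

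**The case against.** The strongest reply is that section 3 is a design summary while 5.1 and 7.6 are the working anaesthesia and dosing instructions, and that additional boluses may be shorthand for any rocuronium after intubation. On that reading the infusion-only conflict disappears. Part of this stands: the infusion-only conflict does depend on a literal reading. But the patient who had only the intubation dose remains in conflict on either reading, and section 3 still permits what 5.1 and 7.6 instruct. No text says which section governs, and section 3 is where the comparison is declared.

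A reader might infer that the ambiguity exposes controls to residual paralysis. The documents do not support that: extubation requires a stable TOF ratio above 0.9 whichever reversal rule is followed.

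A reader might also infer that group B has conversion as its only recourse, or that the missing pressure step must be a mistake. Neither follows. Block adjustment comes before conversion, and sections 11.3 and 13.2 describe raising pressure when visibility is compromised at low pressure, so having no pressure step in controls may be intended. If so, 8.3 should say it.

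Finally, the extra 0.6 mg/kg could be expressed as hours of infusion to suggest a materially different treatment in group A. That would mislead, because both sections titrate the infusion to PTC 1-2 and the target depth is the same. The missing per-hour unit is typographical, since 7.3 and 7.5 supply it.

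**Conclusion.** The point holds as an inconsistency in three operative rules and should be corrected. Control reversal is contradictory for unrecovered controls without an additional bolus, in unknown number. The rescue rule names two non-existent groups and gives group B no step against three in group A. Group A's bolus total is 1.2 or 0.6 mg/kg depending on the section followed.

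These conclusions rest on the current text alone; the infusion-only row additionally needs boluses to mean boluses. It would be tempting to say that the treatment comparison is compromised. The documents do not support that: starting pressure (8 versus 14 mmHg) and block depth (PTC 1-2 versus TOF 1-2) are stated consistently, and no endpoint, power or sample-size consequence is shown.

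**What to change.** **Reversal.** State one rule in sections 3, 5.1 and 7.6. The TOF-ratio rule is preferable because it depends on measured recovery and two of the three texts already share it: controls receive sugammadex 2 mg/kg after skin closure if the TOF ratio is 0.9 or lower, and none if it is above 0.9. The sponsor should confirm this choice, since it replaces the default of spontaneous recovery declared in section 3. If section 3 is what was meant, 5.1 and 7.6 should be changed instead.

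**Rescue.** In 8.3, delete groups C and D and state that rescue in group A runs from 8 to 14 mmHg. For group B, either give a usable cap, for example the 16 mmHg now assigned to C and D, or state that it has no pressure rescue and relies on block adjustment and then conversion. Note that the planned venous plexus step (14 and 20 mmHg) is separate from this rule.

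**Dosing.** Put the second 0.6 mg/kg group A bolus in both 5.1 and 7.6 or in neither, and write the infusion in mg/kg/h with the same range.

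**Cost.** Amendment wording only: the reversal text, one rescue sentence and one dosing line. No extra patients, procedures or data fields, and no change in sample size. The reversal and group B choices do settle what some controls receive, so they are decisions for the sponsor rather than copy-editing.
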